7.2.6 Day 16-28 for Subjects Still Hospitalized: SMT and Daily Evaluations

All subjects receive continued SMT.

Daily assessments include the following:

- Ordinal Scale assessment
- NEWS ([Appendix 2](#))
- Clinical features key symptoms: fever, cough, shortness of breath, fatigue, myalgia etc.
- Vital signs (temperature, systolic and diastolic blood pressure, pulse, respiratory rate)
- Record any supplemental oxygen administration (type, %, flow start/end date/time)
- If subject requires mechanical ventilation post randomization: Record mechanical ventilation (start/end date/time)
- Record oxygen saturation (specify on or off oxygen supplementation)
- Record SAEs and TEAEs
- Record standard care concomitant medications

7.2.7 Day 29±1 day – All Subjects

Assessments include the following:

GRIFOLS Bioscience Industrial Group	Number	BIG-CL-PRT-000019	Version	6.0	Status	Effective	Effective Date	08-Dec-2021	Page	56 of 94
	GC2006 -A Multicenter, Randomized, Open-label, Parallel Group Pilot Study to Evaluate the Safety and Efficacy of Prolastin®-C Liquid plus Standard Medical Treatment (SMT) versus SMT alone in Hospitalized Subjects with									

 • Ordinal Scale assessment • NEWS (Appendix 2) • Clinical features key symptoms: fever, cough, shortness of breath, fatigue, myalgia etc. • Vital signs (temperature, systolic and diastolic blood pressure, pulse, respiratory rate) • Record any supplemental oxygen administration (type, %, flow start/end date/time) • If subject requires mechanical ventilation post randomization: Record mechanical ventilation (start/end date/time) • Record oxygen saturation (specify on or off oxygen supplementation) • Record hospital discharge date • If subject requires ICU admission post randomization: Record ICU discharge date • Record SAEs and TEAEs • Record standard care concomitant medications • Respiratory sample for quantitative measurement of SARS-CoV-2 viral load by NAT or PCR (real-time RT-PCR) (obtained via nasopharyngeal swab) • Sample for quantitative measurement of IgM and IgG antibodies to SARS-CoV-2 (if antibodies cannot be determined at the site store serum samples frozen at -70°C for later analysis at an external lab) • Serum Chemistry (creatinine, albumin, ALT, total bilirubin, LDH) • Calculate eGFR using the Cockcroft-Gault formula. • Hematology: absolute neutrophil & lymphocyte count and standard hematology (hemoglobin, hematocrit, platelet count, leukocyte count with differential) • Assessment of ARDS (Berlin Criteria) (Appendix 3) • Ferritin, D-dimer, CRP • Cytokine panel (IL-1β, IL-10, IL-6, IL-8, IL-2, interferon γ, and TNF-α). Note: serum samples must be stored at -70° C for later analysis at a reference laboratory. • Levels of alpha 1-PI (AAT) activity and antigen; both plasma (sodium citrate) and serum samples to be stored at - 70° C for measurement of both antigenic content and functional activity (potency). 										

7.2.8 Day 60 \pm 2 days and Day 90 \pm 2 days Phone Checks – All Subjects

- Phone Checks will be performed on Day 60 and Day 90:
- to confirm the subject's vital status (living or deceased)
- to record any hospital re-admissions
- to record any SAEs/non-serious AEs after the Day 29 Final Clinic Visit

7.2.9 Description of Laboratory Tests and Procedures

Table 7-1 Name, Description, and Location of Laboratory Tests and Procedures

provides a summary of the laboratory tests conducted for this study.

Table 7-1 Name, Description, and Location of Laboratory Tests and Procedures

Test Panel ^a		Description	Location
Effective Date	Page		
Hematology		Absolute neutrophil & lymphocyte count; Basic hematology: Hemoglobin, hematocrit, platelets, white blood cell (WBC) count with differential	Local
Chemistry		Creatinine, albumin, alanine aminotransferase (ALT), total bilirubin, lactate dehydrogenase (LDH)	Local
Markers of inflammation		C-reactive protein (CRP), D-dimer, ferritin	Local
Cytokine panel		Cytokine panel includes IL-1 β , IL-10, IL-6, IL-8, IL-2, interferon γ , and tumor necrosis factor- α (TNF- α). Note: serum samples must be stored at -70° C for later analysis at a reference laboratory.	Central
Quantitative measurement of SARS-CoV-2 viral load by NAT or PCR (RT-PCR)		Quantitative NAT or PCR (real-time RT-PCR) in respiratory samples (obtained via nasopharyngeal swab)	Central
Quantitative measurement of IgM and IgG antibodies to SARS-CoV-2		Quantitative IgM and IgG antibody levels by ELISA, IFA, or other assay methodology (if antibodies cannot be determined at the site store serum samples frozen at -70°C for later analysis at an external lab)	Central
AAT (activity & antigen)		Levels of alpha 1-PI (AAT) activity and antigen; both plasma (sodium citrate) and serum samples to be stored at -70° C for measurement of both antigenic content and functional activity (potency).	Store local/ Central analysis

8 ASSESSMENT OF SAFETY

8.1 Safety Parameters

The safety and tolerability of Liquid Alpha₁-PI (Human) in subjects with COVID-19 will be evaluated in this study. Safety endpoints will include:

- Cumulative incidence of treatment-emergent SAEs and potentially related SAEs through Day 90 phone check
- Cumulative incidence of Grade 3-5 TEAEs and potentially related severe TEAEs through Day 29 as defined in the CTCAE, US Department of Health and Human Services, NIH, and NCI
- Cumulative incidence of all TEAEs and potentially related TEAEs through Day 29

In this clinical study, disease progression is defined as the worsening of a subject's condition attributable to the disease for which the investigational product is being studied. It may be an increase in the severity of the targeted disease and/or increases in the symptoms of the targeted disease. Anticipated symptoms of COVID-19 include fever, cough, hypoxia, dyspnea, hemoptysis, myalgia, fatigue, pharyngitis which may develop at any time during the course of the disease. The development of COVID-19 symptoms during the clinical study should not be recorded as individual TEAEs, unless there is evidence suggesting a causal relationship between blinded Liquid Alpha₁-PI (Human)/Placebo and the TEAE.

GRIFOLS Bioscience Industrial Group	Number	BIG-CL-PRT-000019	Version	6.0	Status	Effective	Effective Date	08-Dec-2021
	GC2006 -A Multicenter, Randomized, Open-label, Parallel Group Pilot Study to Evaluate the Safety and Efficacy of Prolastin®-C Liquid plus Standard Medical Treatment (SMT) versus SMT alone in Hospitalized Subjects with Hypersensitivity reactions, including anaphylaxis, may occur. Monitor vital signs and observe the subject carefully throughout the infusion.	Page	58 of 94					

8.2 Methods and Timing for Assessing, Recording, and Analyzing Safety Parameters

The Schedule of study procedures is located in [Appendix 1](#).

TEAEs will be recorded in source documents and on Grifols form for recording of TEAEs.

8.3 Procedures for Eliciting Reports of and for Recording and Reporting Adverse Event and Intercurrent Illnesses

8.3.1 Warnings/Precautions

Hypersensitivity reactions, including anaphylaxis, may occur. Monitor vital signs and observe the subject carefully throughout the infusion.

Individuals with known selective or severe IgA deficiency who have known antibodies against IgA should not receive Liquid Alpha₁-PI (Human) since these subjects may experience severe reactions, including anaphylaxis, to IgA which may be present in the preparation.

Since Liquid Alpha₁-PI (Human) can cause a transient increase in blood volume, particular caution is necessary in subjects with severe heart failure and subjects at risk of circulatory overload.

When medicines are made from human plasma, certain measures are put in place to prevent infections being passed on to subjects. These include:

- Careful selection of blood and plasma donors to make sure those at risk of carrying infections is excluded
- The testing of each donation and pools of plasma for signs of virus/infections
- The inclusion of steps in the manufacturing of plasma derivatives with virus inactivation/removal capacity

However, despite these measures, when medicines prepared from human blood or plasma are administered, the possibility of passing on infection cannot be totally excluded. This also applies to any unknown or emerging viruses or other types of infections.

8.3.2 Adverse Event Monitoring

Subjects must be carefully monitored for AEs particularly in terms of their seriousness, severity, and causal relationship to the study drug.

GRIFOLS	Number	BIG-CL-PRT-000019	Version	6.0	Status	Effective	Effective Date	08-Dec-2021
	GC2006 -A Multicenter, Randomized, Open-label, Parallel Group Pilot Study to Evaluate the Safety and Efficacy of Prolastin®-CL Liquid plus Standard Medical Treatment (SMT) versus SMT alone in Hospitalized Subjects with						Page	59 of 94

8.3.3 Adverse Event Definitions

8.3.3.1 Adverse Events

An AE is defined as any untoward medical occurrence in a subject or clinical investigation subject administered a medicinal product or study treatment and which does not necessarily have a causal relationship with this administration. An AE can therefore be any unfavorable and unintended sign (including any abnormal laboratory finding, for example), symptom, or disease temporally associated with the use of a medicinal product, whether or not considered related to the medicinal product.

In this clinical study, disease progression is defined as the worsening of a subject's condition attributable to the disease for which the investigational product is being studied. It may be an increase in the severity of the targeted disease and/or increases in the symptoms of the targeted disease. Anticipated symptoms of COVID-19 include fever, cough, hypoxia, dyspnea, hemoptysis, myalgia, fatigue, pharyngitis, which may develop at any time during the course of the disease. The development of COVID-19 symptoms during the clinical study should not be recorded as individual TEAEs, unless there is evidence suggesting a causal relationship between blinded Liquid Alpha₁-PI (Human)/Placebo and the TEAE.

8.3.3.2 Suspected Adverse Drug Reactions/Adverse Reactions

All noxious and unintended responses to a medicinal product or study treatment related to any dose should be considered suspected ADRs (i.e., potentially drug related AEs). The phrase "responses to a medicinal product" means that a causal relationship between a medicinal product or study treatment and an AE is at least a reasonable possibility.

8.3.4 Assessment of Causality of Adverse Event

The investigator is required to provide a causality assessment for each AE reported to the sponsor. The assessment of the causal relationship of an AE to the administration of IP must be a clinical decision based on all available information at the time of the completion of the CRF and/or SAE Report Form. The sponsor will consider the investigator's causality assessment and also provide its own assessment.

Causal relationship to the IP will be established according to medical judgment on whether there is a **reasonable possibility of a causal relationship between the AE and the IP administration.**

GRIFOLS Bioscience Industrial Group	Number	BIG-CL-PRT-000019	Version	6.0	Status	Effective	Effective Date	08-Dec-2021
	GC2006 -A Multicenter, Randomized, Open-label, Parallel Group Pilot Study to Evaluate the Safety and Efficacy of Prolastin®-CL Liquid plus SMT alone in Hospitalized Subjects with						Page	60 of 94

The investigator must determine and classify the AE causality according to the following categories:

Unrelated/Not related: there is not a reasonable possibility of causal relationship between the AE and the IP.

Possibly related: there is evidence to suggest a causal relationship between the IP and the AE.

Definitely related: there is a reason to conclude that the IP caused the AE.

Criteria to assess the causal relationship should take into account of the following conditions: 1) a plausible temporal sequence from the IP administration to the AE onset; 2) whether the event follows a known response pattern to the suspected treatment; 3) whether the AE could be reasonably explained by the subject's clinical state, comorbidities, or concomitant medications, as well as 4) the occurrence of improvement on stopping/reducing the treatment (positive dechallenge) and/or reappearance of the event on repeated exposure (positive rechallenge).

For expedited safety reporting purposes, AEs assessed as either "definitely related" or "possibly related" will be considered POTENTIALLY RELATED or just RELATED.

Any AE reported prior to the first administration of the IP will be considered a non-treatment-emergent AEs and causal relationship will always be "Unrelated/Not related."

8.3.5 Severity of Adverse Event or Suspected Adverse Drug Reaction

Adverse events and suspected ADRs (i.e., potentially drug related AEs) will be classified depending on their severity according to the following definitions:

Mild: an AE which is well tolerated by the subject, causing minimum degree of malaise and without affecting normal activities.

Moderate: an AE that interferes with the subject's normal activities.

Severe: an AE that prevents the subject from performing their normal activities.

This category is further subdivided into Grade 3-5 AEs defined according to CTCAE criteria, US Department of Health and Human Services, NIH, and NCI.

Adverse events and suspected ADR severity gradation must be distinguished from AE and suspected ADR seriousness gradation, which is defined according to event consequence. For example, headache can be mild, moderate or severe but not necessarily serious in all these cases.

The investigator will be responsible for assessing the AE and suspected ADR intensity during the clinical trial, taking into account current criteria included in this section.

8.3.6 Expectedness of Adverse Event or Suspected Adverse Drug Reaction (Reference Safety Information)

An AE or suspected ADR (i.e., potentially drug related AE) is considered “unexpected” if the nature, seriousness, severity or outcome of the reaction(s) is not consistent with the reference information, which is the Liquid Alpha₁-Proteinase Inhibitor (Human) (Prolastin-C Liquid) Investigator’s Brochure. The expectedness shall be determined by the sponsor for any serious ADRs (potentially related SAEs) according to the reference document for expedited safety reporting purposes.

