4.1.4 Safety Endpoints

The safety endpoints include:

- Cumulative incidence of treatment-emergent serious adverse events (SAEs) and potentially related SAEs through Day 90 phone check
- Cumulative incidence of Grade 3-5 treatment-emergent adverse events (TEAEs) and potentially related severe TEAEs through Day 29 as defined in the Common Terminology Criteria for Adverse Events (CTCAE), US Department of Health and Human Services, National Institutes of Health (NIH), and National Cancer Institute (NCI)
- Cumulative incidence of all TEAEs and potentially related TEAEs through Day 29

In this clinical study, disease progression is defined as the worsening of a subject's condition attributable to the disease for which the investigational product is being studied. It may be an increase in the severity of the targeted disease and/or increases in the symptoms of the targeted disease. Anticipated symptoms of COVID-19 include fever, cough, hypoxia, dyspnea, hemoptysis, myalgia, fatigue, pharyngitis, which may develop at any time during the course of the disease. The development of COVID-19 symptoms during the clinical study should not be recorded as individual TEAEs, unless there is evidence suggesting a causal relationship between blinded Liquid Alpha₁-PI (Human)/Placebo and the TEAE.

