8.3.8 Adverse Event Documentation

All AEs and SAEs occurring on Day 1 through the Day 29 (± 1 day)/Final Visit must be fully recorded in the subject's medical record and CRF, and paper SAE report form (if serious).

At the time of the Day 60 (± 2 days) and Day 90 (± 2 days) Phone Checks any additional SAEs/non-serious AEs will also be collected and recorded.

It is the responsibility of the investigator to ensure that AEs are appropriately recorded.

AEs will be collected through directly observed events or spontaneously volunteered by the subject. Clearly related signs, symptoms and abnormal diagnostic procedures should preferably be grouped together and recorded as a single diagnosis or syndrome wherever possible.

The following variables must be recorded:

- The verbatim term (a diagnosis is preferred)
- Date/time of onset
- Date/time of resolution
- Severity (mild, moderate, severe [Grade 3 to Grade 5])
- Causality (unrelated, possibly related, definitely related)*
- Seriousness (yes, no)
- Action taken (with regard to IP)
- Other action (to treat the event)
- Outcome and sequel (follow-up on AE)

*Causality assessment will be made only when the AE occurs after the subject has initiated at least one infusion of the IP. An AE occurring before subject's exposure to IP will be always labeled as "unrelated".

For AEs that occur during infusions, the infusion rate in effect at the time of onset of the AE, the time of onset of the AE and the time of AE change materially in intensity and/or resolve will be captured.

In addition to the investigator's own description of the AE, each AE will be encoded according to the Medical Dictionary for Regulatory Activities (MedDRA).

For example, a laboratory test abnormality considered clinically significant, eg, causing the subject to withdraw from the study, requiring treatment or causing apparent clinical manifestations, or judged clinically significant in the context of the subject's medical history by the investigator, should be reported as an AE. Each event must be described in detail along with start and stop dates, severity, relationship to IP, action taken and outcome. Each

event must be adequately supported by documentation as it appears in the subject's medical or case file.

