8.5 Study-Independent Safety Review Committee (SISRC) and Stopping Rules

Grifols will utilize a SISRC whose members (from Grifols) will be impartial and independent of the clinical trial team, and will consist of a global pharmacovigilance representative, a medical director, and a third individual knowledgeable in the epidemiological field or knowledgeable in the therapeutic area or a statistician. The SISRC will review relevant safety information from the study as outlined in the SISRC Charter. At a minimum, after the first 20 subjects are enrolled and have completed treatment, the SISRC will conduct an initial safety review. The SISRC will perform a causality review of all TEAEs and SAEs. The SISRC will be notified of relevant SAEs inasmuch as feasible within 24 hours, but no later than 3 days.

Stopping rules are delineated below. Any change to the study stopping rules must be reviewed by the FDA. If the study is suspended it will not be re-opened without prior FDA approval.

Stopping criteria for temporary suspension of further study enrollment/recruitment pending full safety investigation by the SISRC are detailed below.

The SISRC will conduct a safety evaluation and study enrollment/recruitment will be temporarily suspended while the safety investigation is undertaken if any one of the following occur:

- 1 death, i.e. at the time of each death, regardless of causality attribution by the Principal Investigator or whether it may be considered COVID-19 related. Pausing enrollment/recruitment after any death will allow the SISRC to perform a full investigation of every fatal event. (Note: Further infusions for subjects already randomized will only be stopped if there is elevated concern by the Principal Investigator or the SISRC that the death is drug related.)
- 1 Grade 4 treatment-emergent AE occurs in any of the first 3 randomized subjects considered potentially related to blinded study drug
- 1 subject develops a Grade 3 hypersensitivity reaction or serious anaphylactic reaction at any time attributable to Liquid Alpha₁-PI (Human)
- 10 subjects develop treatment-emergent AEs in the same system organ class that are \geq Grade 2 severity (CTCAE grading criteria)
- 2 subjects develop treatment-emergent Grade 4 serious AEs of the same kind in the first 20 subjects
- 5 subjects develop Grade 3 or 4 treatment-emergent AEs that are at least possibly related to blinded study drug at any time during the study

GRIFOLS	Number	BIG-CL-PRT-000019

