In the remaining summary tables, the incidence of TEAEs will be calculated by dividing the number of subjects who have experienced the event by the total number of subjects. Thus, the incidence of TEAEs is shown in terms of the total number of subjects and not in terms of the total number of episodes. If a subject has repeated episodes of a particular TEAE, only the most severe episode, or the episode with the strongest causal relationship to IP, will be counted in the summary tables.

A subject with more than one type of TEAE in a particular SOC or PT will be counted only once in the total of subjects experiencing TEAEs in that particular SOC or PT.

All occurrences of all AEs and SAEs will be listed for each subject, grouped by treatment group. The listing will contain the following information: treatment group, verbatim term, SOC, PT, severity (mild [Grade 1], moderate [Grade 2], severe [Grade 3-5]), relationship to IP, date/time and day of onset, date/time and day of resolution, action taken with regard to IP, whether additional non-drug or drug treatment was given to treat the adverse event, the outcome, whether the event was an SAE, whether it led to study withdrawal, whether it occurred during IP infusion, and whether it is a TEAE. Listings will be sorted by treatment group, subject identification number, onset date, SOC, and PT. If the onset date is completely missing, then these events will be presented first. If the onset date is missing a month or a day, then these events will be presented before any complete dates.

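### AE severity is rated by effect on normal activities and CTCAE only subdivides 'severe', so the Grade 2 CTCAE stopping rule has no CTCAE Grade 2 data behind it and Grades 3-5 sit behind a functional gate

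*Protocol*

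**What the plan says.** **Severity scale.** Protocol 8.3.5 defines three categories by effect on normal activities. Mild is well tolerated, causes minimal malaise and leaves activities unaffected. The next two read "Moderate: an AE that interferes with the subject's normal activities" and "Severe: an AE that prevents the subject from performing their normal activities". CTCAE then appears once, attached to the severe category: "This category is further subdivided into Grade 3-5 AEs defined according to CTCAE criteria". The investigator is to assess intensity "taking into account current criteria included in this section".

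**What is recorded.** The list of variables in Protocol 8.3.8 has the same form: "Severity (mild, moderate, severe [Grade 3 to Grade 5"]). No grade is attached to mild or moderate.

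**What uses the grade.** The second safety endpoint (Protocol 4.1.4 and 8.1; SAP 2.2.4) is the incidence of Grade 3-5 events "as defined in the Common Terminology Criteria for Adverse Events (CTCAE"). Footnote d of the schedule (Protocol Appendix 1; SAP Appendix A) also says that CTCAE defines Grades 3-5. Among the stopping criteria in Protocol 8.5, one suspends enrolment when 10 subjects have treatment-emergent AEs in one system organ class at or above "Grade 2 severity (CTCAE grading criteria").

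**SAP.** Section 7.2.2 refers back to Protocol 8.3.5. Section 7.2.5 describes the AE listing as showing "severity (mild [Grade 1], moderate [Grade 2], severe [Grade 3-5"]).

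**The concern.** A rule or endpoint stated on a published grading scale should be fed by grades on that scale. Here the only route to a CTCAE grade runs through a different, functional judgement. The Grade 2 stopping rule therefore depends on an assessment that the plan never asks for, and the Grade 3-5 endpoint depends on one that is made only for a functionally selected subset of events. The uses at stake are suspension of enrolment for a safety investigation, the Grade 3-5 endpoint, and the SAP tables of events at Grade 3 and above (SAP 7.2.5, items i.d, vi and vii).

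**Working it through.** The documents give no figure that depends on the severity scale, so there is nothing to reproduce. The check is a comparison of passages, followed by an illustration on assumed rates.

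**1. Which grades are assessed, and how?**

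| Grade | Assigned by (Protocol 8.3.5, 8.3.8) | Label in SAP 7.2.5 listing | Used by |
|---|---|---|---|
| 1 | functional mild; no CTCAE instruction | mild | listing and severity tables |
| 2 | functional moderate; no CTCAE instruction | moderate | 10-subject stopping rule, which names CTCAE |
| 3-5 | functional severe first, then CTCAE | severe | safety endpoint; grade-based stopping criteria |

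For Grade 2, a count on the stated scale cannot be formed from the data described. What can be counted is functional moderate or worse.

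**2. Grades 3-5.** Section 8.3.5, the endpoint and footnote d agree that CTCAE defines these grades. They differ on entry: 8.3.5 requires that the event first prevent normal activities, while the endpoint and footnote d set no such condition. Two kinds of event fall between them.

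- *CTCAE Grade 3 or higher, but not preventing normal activities.* Protocol 8.3.8 makes a laboratory abnormality reportable as an AE if, among other grounds, the investigator judges it clinically significant in the light of the medical history. No effect on activities is needed. Such an AE can be rated below severe and so may go without a CTCAE grade.
- *Preventing normal activities, but below CTCAE Grade 3.* The severe category is divided only into Grades 3-5, and this event meets none of those definitions. The text gives it no place.

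**3. Reach.** Section 8.5 lists eight criteria. Five use a grade: Grade 4 in the first 3 subjects; Grade 3 hypersensitivity; Grade 2 or above in 10 subjects; Grade 4 serious events in the first 20; Grade 3 or 4 in 5 subjects. Only the Grade 2 rule names CTCAE. The other three (any death; definitely related serious events of the same kind; an unanticipated signal) use no grade. One of the three safety endpoints uses a grade.

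**4. Sensitivity of a count rule to the scale (illustration only).** Assume n = 100 subjects, independent outcomes, a true CTCAE event rate p, and a recorded count equal to a multiple s of the true rate. The probability of triggering at r subjects is P(X ≥ r), with X ~ Binomial(100, p·s). Neither p nor s is in the documents.

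| Rule | p | s = 1 | s = 0.9 | s = 0.75 | s = 0.5 |
|---|---|---|---|---|---|
| 10 subjects, Grade 2 or above, one organ class | 0.10 | 0.549 | 0.412 | 0.217 | 0.028 |
| same | 0.15 | 0.945 | 0.883 | 0.700 | 0.217 |
| 5 subjects, related Grade 3 or 4 | 0.05 | 0.564 | 0.470 | 0.321 | 0.106 |
| same | 0.08 | 0.910 | 0.854 | 0.723 | 0.371 |

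Error can also run upward. With p = 0.10 and s = 1.25 the recorded rate is 0.125, and the 10-subject rule triggers with probability 0.816 instead of 0.549.

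**The case against.** The best defence is that the passages can be read together: severe means CTCAE Grade 3-5, moderate means Grade 2 and mild means Grade 1. Section 8.3.8 and the SAP listing both pair severe with Grades 3-5, and footnote d has no functional gate. This may well be what was intended. It does not remove the problem. Severe then has two definitions that need not agree, and nothing tells the investigator to apply CTCAE to moderate events.

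A second defence is that other safeguards exist. Laboratory values are summarised with shift tables whatever the AE grade (SAP 7.3) and enter the interim safety analysis (SAP 8.1). The safety review committee reviews causality of all treatment-emergent events and can act on an unanticipated signal (Protocol 8.5). Serious events are defined without reference to activities (Protocol 8.3.7). These points stand and limit the harm, but none of them supplies the count that the Grade 2 rule needs.

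A reader might infer more than the text supports:

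- *That the whole Grade 3-5 endpoint runs on a non-CTCAE scale.* It does not. Grades within severe are CTCAE grades; the fault is the gate.
- *That a functionally severe event must be given Grade 3 or higher even if CTCAE would grade it 2.* No passage says so. Such an event is left without a place.
- *That any laboratory AE causing no limitation is automatically mild.* Mild also requires good tolerance and minimal malaise, and some reportable laboratory AEs are those needing treatment or causing symptoms.
- *That inpatients would be over-graded because illness already limits their activity.* Section 8.3.5 asks what the AE prevents, not what the underlying illness prevents.
- *That the CRF itself omits Grades 1 and 2.* Section 8.3.8 lists variables; the CRF page and the committee charter are not in the documents.

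**Conclusion.** The point holds in a limited form. As written, the Grade 2 stopping rule names CTCAE but would be fed by functional moderate-or-worse ratings. The Grade 3-5 endpoint and the criteria using Grade 3 or 4 carry, or may carry, a functional entry condition that the endpoint's own definition lacks. This is a conflict between passages rather than a lack of detail.

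Its size is unknown. It depends on how often functional and CTCAE ratings disagree, which turns on CTCAE content that the documents do not reproduce, and the disagreement could move counts either way. The probabilities above show only that a count rule responds strongly to such disagreement; they do not estimate its effect in this trial. The conclusion assumes that sites follow 8.3.5 as written and that neither the CRF page nor the charter adds an instruction to grade every AE by CTCAE.

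**What to change.** Reconcile Protocol 8.3.5, 8.3.8, 8.5 and Appendix 1 footnote d with SAP 7.2.5:

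- Record a CTCAE grade (1-5) directly for every AE, including laboratory AEs.
- Use that grade for the Grade 3-5 endpoint and for the grade-based stopping criteria.
- Either derive mild, moderate and severe from the grade by the mapping the SAP listing already prints, or keep the functional rating as a separate descriptor that does not decide whether an event is graded.
- Leave the stopping thresholds as they are.

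The cost is protocol wording, one CRF field, site retraining and regrading from source of AEs already entered. Section 8.5 requires FDA review of any change to the stopping rules, so review may be needed if the clarification is treated as such a change.
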